2.5.2 Statistical hypothesis, model, and method of analysis

Primary efficacy variable 1

The null hypothesis is that the mean percent change from baseline in LDL-C at Day 330 for "inclisiran first" implementation strategy and usual care groups are equal. The alternative hypothesis is that the mean percent change from baseline in LDL-C at Day 330 for "inclisiran first" implementation strategy group is not equal to that of the usual care group.

Primary efficacy variable 1 will be analyzed using mixed-effects model repeated measures (MMRM) with treatment, visit (Day 90, Day 180, Day 270, Day 330), baseline, [REDACTED], [REDACTED], treatment-by-visit interaction, and baseline-by-visit interaction as explanatory variables. An unstructured covariance matrix will be assumed for this model. Least-squares mean of each treatment group, least-squares mean treatment difference, two-sided 97.5% confidence intervals for the treatments, two-sided 97.5% confidence interval for the treatment difference, and p-value based on the fitted MMRM will be reported for each applicable visit (day). If the p-value based on a two-sided test for treatment effect at Day 330 is < 0.025 and the corresponding least squares mean treatment difference ("inclisiran first" implementation strategy – usual care) is less than 0, statistical significance in favor of "inclisiran first" implementation strategy is shown. All efforts will be made to follow up participants until the end of the study. Participants will be expected to follow the visit schedule and assessments even after discontinuation of study treatment. Data after participants discontinued study treatment will be used in the analysis ("retrieved dropout").

The primary analysis of primary efficacy variable 1 will be based on the FAS. The primary analysis of this variable will be repeated for the Per-Protocol Set, Restricted Set 1, and Restricted Set 2.

Primary efficacy variable 2

The null hypothesis is that the difference ("inclisiran first" implementation strategy – usual care) in the proportion of participants who discontinue statin therapy at Day 330 is at least 0.15 (non-inferiority margin). The alternative hypothesis is that the difference ("inclisiran first" implementation strategy – usual care) in the proportion of participants who discontinue statin therapy at Day 330 is less than 0.15.

For primary efficacy variable 2, a one-sided 98.75% confidence interval for treatment difference ("inclisiran first" implementation strategy – usual care) in the proportion of participants who discontinued statin therapy at Day 330 will be computed using the normal approximation to the binomial distribution. Non-inferiority of the "inclisiran first" implementation strategy to usual care will be declared if the upper limit of the confidence interval does not exceed the non-inferiority margin of 0.15. The difference in proportions and associated two-sided 97.5% confidence interval will also be provided.

The primary analysis of primary efficacy variable 2 will be based on the FAS excluding participants who had medical history of statin intolerance. The primary analysis of this variable will be repeated for the Per-Protocol Set and Restricted Set 2.

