Data analysis	
The primary efficacy variables are the following:
 
 
1. Percent change from baseline in LDL-C
 
2. Discontinuation of statin therapy (i.e., no statin use <math>\geq</math> 30 days before the end-of-study visit) (yes, no)
 
 
The primary analysis time point for both primary efficacy variables is at Day 330.
 
Primary efficacy variable 1 will be analyzed using mixed-effects model repeated measures (MMRM) with treatment, visit, baseline, [REDACTED] treatment-by-visit interaction, and baseline-by-visit interaction as explanatory variables. An unstructured working correlation matrix will be assumed for this model. Least-squares mean of each treatment group, least-squares mean treatment difference, two-sided 97.5% confidence interval for the treatment difference, and p-value based on the fitted MMRM will be reported for each applicable visit (day). If the p-value based on a two-sided test for treatment effect at Day 330 is <math><</math> 0.025 and the corresponding least squares mean treatment difference ("inclisiran first" implementation strategy – usual care) is less than 0, statistical significance in favor of "inclisiran first" implementation strategy is shown.
 
For primary efficacy variable 2, a one-sided 98.75% confidence interval for treatment difference ("inclisiran first" implementation strategy – usual care) in the proportion of participants who discontinued statin therapy at Day 330 will be computed using the normal approximation to the binomial distribution. Non-inferiority of the "inclisiran first" implementation strategy to usual care will be declared if the upper limit of the confidence interval does not exceed the non-inferiority margin of 15%.
 
The secondary efficacy variables are the following:
 
 
1. Absolute change from baseline in LDL-C
 

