#### 4.1.1 Rationale for choice of background therapy

Participants are required to be on maximally tolerated statin therapy at the time of identification and screening without plans to adjust lipid lowering therapy at that point in time.

Other than inclisiran in the inclisiran arm, therapies will not be made available by the sponsor. The trial could be criticized if patients in the usual care arm could not receive non-statin therapies because of insurance issues. To address the bias that may arise due to differences in access to therapies, randomization will be stratified by [REDACTED] as described in [Section 6.3.2](#) of the protocol, and various statistical methods will adjust for [REDACTED] at baseline (yes, no). Importantly, valuable insights can be gathered from studying the implementation of an “inclisiran first” implementation strategy versus usual care without providing access to therapies:

- It increases the external validity of the trial
- It enables the study of implementation of an effective LDL-C lowering therapy in the absence of access barriers
- It enables examination of implementation of inclisiran in [REDACTED]

Inclisiran will not be excluded from the comparator group post-approval to avoid withholding of an approved therapy if deemed necessary by the treating physician, although the use of inclisiran in the comparator group is discouraged. Inclisiran will not be provided by the sponsor to participants in the comparator group. It is assumed based on historical and anticipated product uptake shortly after launch that potential inclisiran treatment in the comparator group will be minimal and thus will not significantly interfere with the study. Participants receiving inclisiran during the trial should not be simultaneously treated with a PCSK9 inhibiting monoclonal antibody since simultaneous use has not been evaluated in registration trials.

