### **6.3.2 Treatment assignment, randomization**

At visit 2, all eligible participants will be randomized via Interactive Response Technology (IRT) to one of the two treatment groups in 1:1 ratio ("inclisiran first" implementation strategy or usual care). The investigator or his/her delegate will contact the IRT after confirming that the participant fulfills all the inclusion/exclusion criteria. The IRT will assign a randomization number to the participant, which will be used to link the participant to a treatment group and will specify a unique medication number for the first package of study treatment to be dispensed to the participant.

The randomization numbers will be generated using the following procedure to ensure that treatment assignment is unbiased. A participant randomization list will be produced by the IRT system provider using a validated system that automates the random assignment of participant numbers to randomization numbers. These randomization numbers are linked to the different treatment groups, which in turn are linked to medication numbers. A separate medication list will be produced by or under the responsibility of Novartis Drug Supply Management using a validated system that automates the random assignment of medication numbers to the package containing the investigational drug(s).

Randomization will be stratified by [REDACTED]. The stratification ensures balanced allocation of participants to treatment groups within the [REDACTED] strata.

The randomization scheme for participants will be reviewed and approved by a member of the Novartis Biometrics group.

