The primary analysis of primary efficacy variable 2 to address the primary objective will be based on the following estimand:

- Population: Defined through appropriate inclusion/exclusion criteria to reflect the targeted population and if a participant was not statin intolerant at the beginning of the trial
- Variable: Discontinuation of statin therapy (yes, no) [The primary analysis time point is at Day 330.]
- Treatment: "Inclisiran first" implementation strategy or usual care
- Remaining intercurrent events: 1. Potential use of inclisiran by participants in the usual care group. This intercurrent event will be ignored in the analysis, as the design of the trial allows for participants in the usual care group to potentially use inclisiran. 2. Discontinuation of study treatment. This intercurrent event will be ignored in the analysis.
- Summary measure: Treatment difference ("inclisiran first" implementation strategy – usual care) in the proportion of participants who discontinue statin therapy

The null hypothesis is that the difference ("inclisiran first" implementation strategy – usual care) in the proportion of participants who discontinue statin therapy at Day 330 is at least 0.15 (non-inferiority margin). The alternative hypothesis is that the difference ("inclisiran first" implementation strategy – usual care) in the proportion of participants who discontinue statin therapy at Day 330 is less than 0.15.

For primary efficacy variable 2, a one-sided 98.75% confidence interval for treatment difference ("inclisiran first" implementation strategy – usual care) in the proportion of participants who discontinued statin therapy at Day 330 will be computed using the normal approximation to the binomial distribution. Non-inferiority of the "inclisiran first" implementation strategy to usual care will be declared if the upper limit of the confidence interval does not exceed the non-inferiority margin of 0.15.

The primary analysis of both primary efficacy variables will be based on the Full Analysis Set.

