1.1 Study design

The study design will be a randomized, two-arm, parallel-group, open-label, multicenter, clinical trial. Approximately 444 participants will be randomized 1:1 to "inclisiran first" implementation strategy or to usual care. Eligible participants have established ASCVD and elevated LDL-C (or non-HDL-C) despite treatment with maximally tolerated statin therapy (but without ezetimibe). The unit of randomization will be the participant. To address the bias that may arise due to differences in access to therapies, randomization will be stratified by [REDACTED] status, and various statistical methods will be adjusted for [REDACTED].

To minimize selection bias and increase generalizability of the results, potential study sites and potentially eligible participants will be identified using electronic data sets (EHR, claims and/or laboratory data). The goal in selecting study sites is to ensure a representative sample of sites in terms of geography, patient population, and lipid management practices. For example, the inclusion of specialized lipid clinics in the trial would lead to more intensive treatment than is typical and would therefore reduce the generalizability of the results. Several tactics will aim to enhance inclusion of minority and medically underserved populations, as these populations are traditionally underrepresented in clinical trials. [REDACTED]

[REDACTED] Second, investigators will explicitly be ority populations. Third, specific barriers to participation will be addressed, including rapid reimbursement (e.g., of transportation costs) and availability of trial materials (such as informed consent forms [ICFs]) in multiple languages). Selected sites will receive a list of patients who could qualify for the trial that is generated based on EHR, claims and/or laboratory data. All participants who meet the eligibility criteria are to be invited using a standardized invite.

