2.5.1 Primary endpoint(s)

The primary efficacy variables are the following:

1. Percent change from baseline in LDL-C
2. Discontinuation of statin therapy (i.e., no statin use \geq 30 days before the end-of-study visit) (yes, no)

The primary analysis time point for both primary efficacy variables is at Day 330.

The following provides additional details on the derivation of primary efficacy variable 2.

If a participant is considered a study completer and has a non-missing visit date for the nominal Day 330 visit recorded, a statin assessment date (to assess if the participant was taking statins at this point in time) will be calculated by subtracting 30 days from the Day 330 visit date (e.g., study Day 300 if the participant completes on study Day 330). The statin assessment date will be compared to the maximum statin end date of all statin medications taken by the participant. If the last statin is recorded as ongoing at study end date, the maximum statin end date will be set to the study end date.

- If the participant was on a statin on or after this statin assessment day (maximum statin end date \geq statin assessment date), the participant will be considered as discontinued statin = 'no.'
- If the participant was not on a statin on and after this statin assessment day (maximum statin end date $<$ statin assessment date), or they were a completer who did not have a Day 330 visit, the participant will be considered as discontinued statin = 'yes.'

All early termination participants will be considered to not be on a statin for this endpoint (the participant will be considered as discontinued statin = 'yes').

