2.5.5 Sensitivity analyses

The sensitivity analysis of primary efficacy variable 1 to address the primary objective will be based on the following estimand:

- Population: Defined through appropriate inclusion/exclusion criteria to reflect the targeted population
- Variable: Percent change from baseline in LDL-C [The primary analysis time point is at Day 330.]
- Treatment: "Inclisiran first" implementation strategy or usual care
- Remaining intercurrent events: 1. Potential use of inclisiran by participants in the usual care group. This intercurrent event will be ignored in the analysis, as the design of the trial allows for participants in the usual care group to potentially use inclisiran. 2. Discontinuation of study treatment (in inclisiran participants). This intercurrent event will be ignored in the analysis.
- Summary measure: Probability of observing the same or a more favorable response with "inclisiran first" implementation strategy relative to usual care

For the above estimand, primary efficacy variable 1 will be analyzed at each time point for the Full Analysis Set using the van Elteren test, adjusting for [REDACTED] (Stokes et al 2012).

The probability of observing the same or a more favorable response (θ_0) with "inclisiran first" implementation strategy relative to usual care will be estimated using nonparametric methods, and the associated 97.5% confidence interval will also be reported (Chen and Kianifard 2000).

For both primary efficacy variable 1 and primary efficacy variable 2, an additional sensitivity analysis will be performed where participants for whom [REDACTED] entered at

randomization (via Interactive Response Technology (IRT)) did not match [REDACTED] entered at baseline (via CRF) were excluded from the analysis.

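### The primary interval for statin discontinuation ignores the randomisation stratum: it is valid, but conservative if the stratum predicts statin stopping

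*SAP*

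**What the plan says.** Protocol 6.3.2 stratifies the randomisation by a redacted factor: "The stratification ensures balanced allocation of participants to treatment groups within the" redacted strata. SAP 1.1 gives the reason: "To address the bias that may arise due to differences in access to therapies, randomization will be stratified by" that factor, and says that various methods will adjust for a factor that is also redacted. Protocol 4.1.1 describes the factor adjusted for as yes/no at baseline.

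For statin discontinuation, SAP 2.5.2 specifies a one-sided 98.75% interval for the treatment difference "in the proportion of participants who discontinued statin therapy at Day 330 will be computed using the normal approximation to the binomial distribution". Protocol 12.4.2 gives the same method ("will be computed using the normal approximation to the binomial distribution"). The Protocol summary adds the decision rule: non-inferiority "will be declared if the upper limit of the confidence interval does not exceed the non-inferiority margin of 15"%. These sentences show no redaction where a stratum term could stand.

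SAP 2.5.5 then adds a check: "For both primary efficacy variable 1 and primary efficacy variable 2, an additional sensitivity analysis will be performed where participants for whom" a redacted item in the IRT did not match the CRF entry are left out.

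**The concern.** One of the two primary tests does not use the strata by which the trial randomises. Stratified allocation removes between-stratum variation from the difference between arms, but a crude variance still counts it. If the stratum predicts stopping, the standard error is too large and the test runs below its nominal level.

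The other readable between-group efficacy models (the MMRM, the van Elteren test, and the linear, logistic and proportional-odds models) each carry a redacted term. Those terms cannot be confirmed to be the stratum. Still, the readable text does not say why this primary variable is treated differently.

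The mismatch check raises a related point. An interval that contains no stratum value gives the same answer under IRT or CRF coding. If the redacted item is the stratification factor, excluding mismatched participants can change the result only by changing who is analysed.

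**Working it through.** **Inputs from the documents.** SAP 3: stopping rate 0.20 in each arm, margin 0.15, one-sided level 0.0125 (z = 2.2414), power 0.90 (z = 1.2816), 1:1 allocation, 10% loss to follow-up plus 10% statin intolerance, 222 randomised per arm. SAP 2.5.2: analysis in the FAS without statin-intolerant participants. SAP 2.5.1: "All early termination participants will be considered to not be on a statin for this endpoint", so they stay in the denominator as stopped.

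**Assumptions.** The documents give no stratum sizes or stratum-specific rates. I take two strata, equal or 25:75, with the same treatment difference in each and stopping-rate gaps of 0 to 30 points. Arm size is 222 × 0.90 = 199.8, about 200. The alternative is 222 × 0.80 = 177.6, about 178.

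**The plan's own figure.** n per arm = (2.2414 + 1.2816)² × 2 × 0.20 × 0.80 / 0.15² = 12.41 × 0.32 / 0.0225 = 176.5, so 177 per arm and 354 in total. Then 177 / 0.80 = 221.25, so 222 per arm and 444 in total. This reproduces SAP 3 with no stratum term, so sizing and analysis agree.

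**Width.** With equal strata and gap g, the within-stratum variance is 0.16 − g²/4, against a crude variance of 0.16:
- g = 0.10: 0.1575, ratio 0.984, crude interval 0.8% wider (1/√0.984)
- g = 0.20: 0.1500, ratio 0.9375, 3.3% wider
- g = 0.30: 0.1375, ratio 0.859, 7.9% wider

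At 200 per arm the crude half-width is 2.2414 × √(0.32/200) = 0.0897. The stratified half-widths are 0.0890, 0.0868 and 0.0831.

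**Error.** At the margin the rates are 0.20 and 0.35. The crude variance sum is 0.16 + 0.2275 = 0.3875 and the within-stratum sum is 0.3875 − g²/2. The error is 1 − Φ(2.2414 × √[0.3875 / (0.3875 − g²/2)]), which gives 0.0125, 0.0120, 0.0107 and 0.0086 for gaps of 0, 10, 20 and 30 points.

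**Exact enumeration**, with simulation agreeing. Each cell runs over the four gaps in order:

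| Setting | Crude error | Crude power | Power change with stratified Miettinen-Nurminen (points) |
|---|---|---|---|
| 20%, equal strata, 200 per arm | 0.0126 / 0.0121 / 0.0108 / 0.0086 | 0.934 / 0.936 / 0.940 / 0.948 | −0.20 / −0.07 / +0.25 / +0.59 |
| 20%, equal strata, 178 per arm | 0.0126 / 0.0121 / 0.0107 / 0.0086 | 0.903 / 0.905 / 0.910 / 0.920 | −0.40 / −0.25 / +0.17 / +0.71 |
| 20%, strata 25:75, 200 per arm | 0.0126 / 0.0122 / 0.0112 / 0.0096 | 0.934 / 0.935 / 0.939 / 0.944 | −0.20 / −0.09 / +0.25 / +0.76 |
| 28%, equal strata, 200 per arm | 0.0121 / 0.0118 / 0.0109 / 0.0093 | 0.866 / 0.867 / 0.871 / 0.877 | +0.06 / +0.25 / +0.84 / +1.67 |

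The 0.0126 at gap 0 comes from the normal approximation, not from leaving out the stratum. The stratified error is between 0.0125 and 0.0128 throughout.

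**Which rate applies.** The documents do not say whether the planned 20% includes early terminators.
- If it does, and the 10% loss is even across strata, no stratum can be below 10%. With equal strata the widest pair is then 10% and 30%, and the 30-point column drops out.
- If it does not, the endpoint rate is 0.10 + 0.90 × 0.20 = 28%, and the gaps shrink to 0, 9, 18 and 27 points. That is the last row.

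**Mismatch check** (assumed 5% or 10% mismatch, 200 per arm, SE = √(0.32/200) = 0.0400). Exclusion widens the crude interval by 1/√(1 − m) − 1 = 2.6% or 5.4%. It also moves the estimate by chance, with SD 0.0400 × √(m/(1 − m)) = 0.9 or 1.3 points. Swapping the CRF stratum into a stratified analysis of all participants moves it by a simulated SD of 0.1 to 0.4 or 0.1 to 0.6 points, for gaps of 0 to 20 points.

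**The case against.** The plan contains no error here. The crude difference estimates the stated summary measure, and the adjustment promise covers various methods, not all. At the planned 20% rate, stratifying costs a little power at gaps of 0 and 10 points and gains only about 0.2 to 0.3 points at a gap of 20. A conservative non-inferiority test is no fault in itself, and a late change to a confirmatory method in an open-label trial has a credibility cost. The item in the mismatch check is blacked out and no purpose is stated for it, so it may simply be a restricted-population check. The two redacted subgroups in SAP 2.2.1 may already report this variable by stratum.

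Most of this stands, and it limits the point to one of efficiency and clarity. It does not remove it. The lost conservatism only returns the error to about its nominal level, and the stratum is already recorded.

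A reader might infer that omitting the stratum makes the test invalid, or that the 0.90 design power is lost. Neither follows: the omission can only lower the error, and 354 was derived without a stratum. A reader might also infer that the factor drives statin stopping. Protocol 4.1.1 speaks of access to non-statin therapies and does not say so.

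**Conclusion.** The point holds as a minor one. The planned interval is valid and matches the sizing, but it does not use the stratified design. Under equal strata and gaps of 10 to 30 points it is 0.8% to 7.9% too wide, with one-sided error of 0.012 down to 0.009 against 0.0125. With no gap there is no cost.

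The power gain from stratifying is about zero or slightly negative at a 20% rate unless the gap is near 20 points or more. It is somewhat larger if the endpoint rate is 28%. All of this depends on assumed strata and on a prognostic effect that the documents do not establish.

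The criticism of the mismatch check is conditional on the redacted item being the stratification factor. That is an inference from its being entered in the IRT at randomisation.

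**What to change.** Before database lock, make the primary analysis of statin discontinuation a risk difference stratified by the IRT randomisation stratum, with Mantel-Haenszel weights and a stratified Miettinen-Nurminen upper limit. Keep the 0.15 margin and the one-sided 98.75% level, and retain the crude interval as a sensitivity analysis. A simple stratified Wald interval is not a good substitute: in simulation at 177 per arm its error was 0.0127 to 0.0136.

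If the redacted item in SAP 2.5.5 is the stratification factor, run the check for this variable by replacing the IRT stratum with the CRF stratum and keeping all participants.

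Cost: the method also stands in the Protocol summary and Protocol 12.4.2, so matching protocol text is needed through a written amendment (Protocol 14.1), plus an entry in SAP 4. About 0.2 to 0.4 points of power are lost if the stratum is not prognostic at a 20% rate, and none at 28%. The error returns to about nominal and is no longer conservative. No new data are needed and the sample size is unchanged.

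If the sponsor keeps the crude method, it should state that this is intended, add the stratified interval as a sensitivity analysis, and say what the mismatch check is for on this variable.
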